9.4.2 Calculation or derivation of safety variables

9.4.2.1 Adverse events

Safety and tolerability will be assessed in terms of AEs (including SAEs), deaths, laboratory data, vital signs, ECGs, and exposure. These will be collected for all patients. Data from all cycles of treatment will be combined in the presentation of safety data. "On treatment" will be defined as assessments between date of start dose and the time period specified in each specific study arm following discontinuation of IP (please see relevant arm appendix for assessment time periods). For AEs, on treatment (or treatment-emergent AEs) will be defined as any AEs that started after dosing or prior to dosing and that worsens following exposure to the treatment.

AEs observed for the time period specified in each specific study arm following discontinuation of study treatment or until the initiation of the first subsequent therapy following discontinuation of treatment (whichever occurs first) will be used for the reporting of the AE summary tables. This will more accurately depict AEs attributable to study

treatment only, as a number of AEs up to the time period specified in each specific study arm following discontinuation of the study agents are likely to be attributable to subsequent therapy. However, to assess the longer term toxicity profile, AE summaries will also be produced containing AEs observed up until the time period specified in each specific study arm following discontinuation of the study agents (ie, without taking subsequent therapy into account). Any events in this period that occur after a patient has received further therapy for cancer (following discontinuation of study treatment) will be flagged in the data listings.

A separate data listing of AEs occurring more than until the time period specified in each specific study arm after discontinuation of IP will be produced. These events will not be included in AE summaries.

9.4.2.2 Safety assessments

For the change from baseline summaries for vital signs, laboratory data, ECGs, and physical examination, the baseline value will be the latest result obtained prior to the start of study treatment.

The QTcF will be derived during creation of the reporting database using the reported ECG values (RR and QT).

$QTcF = QT / RR^{(1/3)}$ where RR is in seconds

Corrected calcium will be derived during creation of the reporting database using the following formulas:

$Corrected\ calcium\ (mmol/L) = Total\ calcium\ (mmol/L) + ([40 - albumin\ (G/L)] \times 0.02)$.

The denominator used in laboratory summaries will only include evaluable patients, in other words, those who had sufficient data to have the possibility of an abnormality.

For example:

- If a CTCAE criterion involves a change from baseline, evaluable patients would have both a pre-dose and at least 1 post-dose value recorded.
- If a CTCAE criterion does not consider changes from baseline, to be evaluable, the patient need only have 1 post dose-value recorded.

The denominator in vital signs data should include only those patients with recorded data.

9.4.3 Calculation or derivation of patient-reported outcome variables

Not applicable.

9.4.4 Calculation or derivation of pharmacokinetic variables

9.4.4.1 Population pharmacokinetics and exposure-response/safety analysis

No population pharmacokinetics and exposure-response/safety analysis is planned for this study given the small number of patients in each arm. However the PK, pharmacodynamics, demographic, safety, and efficacy data collected in this study may also be combined with similar data from other studies and explored using population PK and/or PK-pharmacodynamic methods. See the individual arm sub-protocol appendix (e.g. Appendix A for Arm A) for details of the PK analysis planned in that arm.

9.4.4.2 Pharmacokinetic analysis

PK concentration data and summary statistics will be tabulated. Individual and mean blood concentration time profiles will be generated. PK parameters will be determined using standard non-compartmental methods. The following PK parameters will be determined after the first and steady-state doses: peak and trough concentration (as data allow). Samples below the lower limit of quantification will be treated as missing in the analyses.

9.4.5

CCI

CCI

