3.2 Secondary objectives

Secondary Objective:	Outcome Measure:
To further assess the preliminary efficacy of each treatment arm in terms of duration of response (DoR), DCR, time to response (TTR), PFS, and OS	DoR, DCR, TTR, and PFS using Investigator assessments according to RECIST 1.1 OS
To assess the pharmacokinetics (PK) of novel combination treatments (Arm A, stages 1 and 2 only, Arm B and Arm C)	Concentration of novel combination treatments in blood

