Tumor evaluation (CT or MRI) [RECIST 1.1] ^{l, m}	X			X	X	q8w ± 1 week after week 12 until confirmed objective disease progression/death (whichever comes first).				Section 6.1 master protocol

^a If laboratory or imaging procedures were performed for other reasons prior to signing consent, these can be used for screening purposes with consent of the patient. However, all screening laboratory and imaging results must have been obtained within 28 days of enrollment.

^b Body weight is recorded at each visit along with vital signs. Vital signs are recorded at every clinic visit. Vital signs should be measured separately for both drugs. For details please check Section 6.2.2 Appendix A.

^c Any clinically significant detected require triplicate ECG results.

^d If screening laboratory assessments are performed within 3 days prior to Day 1 (first infusion day), they do not need to be repeated at Day 1. Serum or plasma chemistry, hematology, and/or LFT monitoring may be performed more frequently if clinically indicated.

^e Free T3 and free T4 will be measured if TSH is abnormal or if there is clinical suspicion of an AE related to the endocrine system.

^f For women of childbearing potential only. A urine or serum pregnancy test is acceptable. Women of childbearing potential are required to have a pregnancy test within 7 days prior to the first dose of study drug and then every 4 weeks. Pregnancy test may occur on Day 1, but results must be available and reviewed by the treating physician or Investigator prior to commencing an infusion.

^g Within 10 minutes of the end of infusion.

- ^h Up to 60 minutes pre-dose.
- ⁱ For AEs/SAEs reported during screening, additional information such as medical history and concomitant medications may be needed.
- ^j During the combination portion of treatment, tremelimumab will be administered first; the durvalumab infusion will start approximately 1 hour (maximum 2 hours) after the end of the tremelimumab infusion. If there are no clinically significant infusion reactions with the first cycle, and at the discretion of the Investigator, then for all other cycles, the durvalumab can be given immediately after the tremelimumab infusion has finished.
- ^k Results for serum or plasma chemistry and LFT monitoring must be available before commencing an infusion (within 3 days) and reviewed by the treating physician or Investigator prior to dosing.

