6.4 Pharmacokinetic and Immunogenicity analysis

Durvalumab and tremelimumab PK concentration data and summary statistics will be tabulated by treatment, analyte and timepoint. Individual and mean blood concentration-time profiles will be generated. No PK parameters will be determined due to sparse sampling.

Immunogenicity results will be analyzed descriptively by summarizing the number and percentage of patients who develop detectable ADAs against durvalumab and tremelimumab.

The immunogenicity titer and presence of neutralizing ADAs will be reported for samples confirmed positive for the presence of ADAs. The effect of immunogenicity on PK, efficacy, and safety will be evaluated, if the data allow.

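### Deleting concentrations below the quantification limit biases PK summaries upward, mainly at the late samples, and would understate any loss of exposure linked to anti-drug antibodies

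*Protocol*

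**What the plan says.** Drug concentration is the outcome measure of a secondary objective (Section 3.2: "Concentration of novel combination treatments in blood"). Section 9.4.4.2 of the master protocol plans tabulated summary statistics and profiles ("Individual and mean blood concentration time profiles will be generated") and, in general, peak and trough values ("The following PK parameters will be determined after the first and steady-state doses: peak and trough concentration (as data allow"). It then fixes the handling of low results: "Samples below the lower limit of quantification will be treated as missing in the analyses". No time point is exempted and no sensitivity analysis is attached.

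Appendix A Section 6.4 describes the Arm A output: "Durvalumab and tremelimumab PK concentration data and summary statistics will be tabulated by treatment, analyte and timepoint". It adds "No PK parameters will be determined due to sparse sampling", which does not agree with the general promise of peak and trough in Section 9.4.4.2. In Arm A the affected quantities are therefore the concentration summaries by time point. The same section plans an antibody evaluation: "The effect of immunogenicity on PK, efficacy, and safety will be evaluated, if the data allow". It does not replace the BLQ rule. Appendix A Section 9 and Appendix B Section 9 both refer back to master Section 9 for statistics.

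**The concern.** A sample reported below the limit tells us that the concentration was low. Setting it to missing makes the chance of loss depend on the value itself, so the remaining summary describes only patients whose drug was high enough to measure. The bias can only be upward, and more follow-up or more patients would not remove it.

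Two outputs are at stake. The first is the set of concentration summaries and mean profiles at late time points. The second is the Arm A evaluation of anti-drug antibodies (ADA) on PK. If antibodies speed up clearance, the patients with the strongest effect are the ones most likely to fall below the limit and be deleted, and nearly all deletions would come from the antibody-positive group.

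**Working it through.** The protocol gives no lower limit, BLQ share or expected concentration, so it has no figure to reproduce. The check has three steps.

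**1. Which samples are at risk.**
- Durvalumab half-life is about 21 days (Appendix A Section 2.6.5.1). The fraction remaining after d days is 2^(-d/21): 2^(-28/21) = 0.40 at 28 days and 2^(-90/21) = 0.05 at 90 days.
- Arm A routine troughs are taken at Cycles 2 and 5 ("Up to 60 minutes pre-dose", Appendix A Table 2), four weeks after a dose. About 40% of one durvalumab dose would remain.
- The later Arm A samples are tremelimumab 12 weeks after its last dose (Table 2, Cycle 7 column) and the 3-month PK samples (Appendix A Table 3). About 5% of durvalumab would remain at 90 days. No tremelimumab half-life is stated.
- AZD1775 pre-dose is on Day 3 during twice-daily dosing (Appendix B Table 5), with a half-life near 10 hours (Appendix B Section 2.4.3). The fraction of one dose left after 12 hours is 2^(-12/10) = 0.44.
- Carboplatin pre-dose is on Day 1 of Cycle 1 and alternate cycles. The Cycle 1 sample precedes any study carboplatin; later ones come about three weeks after the previous infusion.
- Arm C samples are post-dose, apart from a Day 7 pre-dose sample on treatment (Appendix C Section 7.2.1).

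The risk is therefore concentrated in the late Arm A samples and carboplatin pre-dose.

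**2. Size of the upward shift.** Assume log-normal concentrations with log-scale SD s = sqrt(ln(1 + CV²)), a share f below the limit, and q = Φ⁻¹(f). After deletion:
- arithmetic mean / true mean = [1 − Φ(q − s)] / (1 − f)
- median / true median = exp{s·Φ⁻¹(f + (1 − f)/2)}

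Example, CV 100% and f = 0.40: s = 0.8326, q = −0.2533, 1 − Φ(−1.0859) = 0.8612, and 0.8612/0.60 = 1.435.

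| BLQ share (assumed) | Mean, CV 30% to 100% | Median, CV 30% to 100% |
|---|---|---|
| 0% | 1.00 | 1.00 |
| 5% | 1.03 to 1.05 | 1.02 to 1.05 |
| 10% | 1.05 to 1.09 | 1.04 to 1.11 |
| 20% | 1.09 to 1.19 | 1.08 to 1.23 |
| 40% | 1.18 to 1.44 | 1.17 to 1.55 |

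PK in Arm A comes from stages 1 and 2 only, planned at 20 patients. The chance of at least one BLQ result among 20 is 1 − 0.95^20 = 0.64 at a 5% rate and 1 − 0.90^20 = 0.88 at 10%.

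**3. Antibody comparison.** Assume CV 50% (s = 0.4724), and a limit and a true ADA-positive to ADA-negative ratio r both expressed relative to the ADA-negative geometric mean. Take r = 0.05 and limit 0.10. Then q = ln(0.10/0.05)/0.4724 = 1.467, so 93% of ADA-positive samples are BLQ and essentially no ADA-negative ones.
- Ratio of arithmetic means after deletion: 0.05 × [1 − Φ(1.467 − 0.472)] / [1 − Φ(1.467)] = 0.05 × 0.1599/0.0711 = 0.112.
- Ratio of geometric means after deletion: 0.123, against 0.053 if BLQ is kept as half the limit.

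Other geometric-mean cases: r = 0.10 with limit 0.10 appears as 0.146 (0.085 with half the limit); r = 0.02 with limit 0.05 appears as 0.060 (0.026 with half the limit). At r = 0.5 nothing material is BLQ and both rules return 0.50.

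**The case against.** The strongest reply is that the rule may touch very little. On the stated half-lives and schedules, routine on-treatment troughs in all three arms look unlikely to be BLQ, so large BLQ shares are conjecture. That stands: it confines the point to the late samples and to antibody-positive patients with very low drug, and the bias is nil if no post-dose sample is BLQ.

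A reader might infer that the rule would hide an antibody effect and produce a false finding of no effect. The numbers do not support that. True ratios of 0.02 to 0.10 appear as 0.060 to 0.146, still a reduction of 85% or more. If every antibody-positive sample were BLQ, the group would be empty, which is visible. The effect is understated, not concealed. The evaluation is also conditional on the data allowing it, its method is not specified, and the earlier antibody counts are redacted, so the number of positive patients cannot be judged.

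A reader might also quote geometric-mean inflation, which is larger. Section 9.5 names the mean, SD, median, minimum and maximum but no geometric mean, so the table in the working uses the mean and median.

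Individual concentrations are to be listed (Section 9.5.5), and summaries show the number of observations. This helps, but listings do not correct the summaries, and a reduced count does not separate BLQ from not sampled. Finally, analyses are descriptive (Section 9.1) and no population PK or exposure-response analysis is planned (Section 9.4.4.1). That limits the importance of the point without making the rule sound.

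**Conclusion.** The concern holds in a limited form. The protocol states a rule that biases concentration means, medians and mean profiles upward wherever post-dose BLQ results occur. The direction is certain; the size is not. Under the assumed log-normal model with CV 30-100%, the arithmetic mean rises about 3-5% at 5% BLQ and 18-44% at 40% BLQ. The exposure lies mainly in the 12-week tremelimumab sample, the 3-month Arm A samples and carboplatin pre-dose. In Arm A, stages 1 and 2 only, an antibody-related fall in exposure to near or below the limit would be understated. This is a minor point on a secondary, descriptive objective, and the ORR analysis does not depend on it.

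**What to change.** Replace the sentence in Section 9.4.4.2 so that BLQ results are not deleted:
- Report the number BLQ at each time point and, in Arm A, by antibody status.
- Set BLQ before the first dose to 0. On the current schedules this affects only carboplatin at Cycle 1 Day 1.
- Keep post-dose BLQ in the summaries under a stated rule, for example half the limit for means and profiles, ranked lowest for the median, and no mean reported when more than half are BLQ.
- Include BLQ samples in the antibody evaluation in Appendix A Section 6.4.
- At the same time, reconcile the parameter statements in Section 9.4.4.2 and Appendix A Section 6.4.

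The cost is a short text change and minor programming; no patient procedure changes. Half the limit is itself an approximation. In the model above its arithmetic mean relative to the truth is [1 − Φ(q − s)] + f·(limit/2)/(true mean), where limit = exp(s·q) and true mean = exp(s²/2). At 40% BLQ this gives 0.976 at CV 100%, 0.925 at CV 50% and 0.886 at CV 30%: a downward bias of 2% to 11%, against 18% to 44% upward under deletion. At 5% BLQ the downward bias is about 1% or less.

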9.4.6 Calculation or derivation of pharmacogenetic variables

Not applicable.

9.5 Methods for statistical analyses

Descriptive statistics will be used for all variables, as appropriate, and will be presented by treatment arm. Continuous variables will be summarized by the number of observations, mean, standard deviation, median, minimum, and maximum. Categorical variables will be summarized by frequency counts and percentages for each category. Unless otherwise stated, percentages will be calculated out of the population total for the corresponding treatment arm.

Baseline will be the last assessment of the variable under consideration prior to the intake of the first dose of IP, except for efficacy variables. For efficacy variables, baseline is defined as the last visit prior to first dose of study treatment.

All data collected will be listed. Efficacy and safety data will be summarized and analyzed based on the FAS. As a sensitivity analysis, efficacy data may also be summarized/analyzed in a subgroup of FAS for patients without important protocol deviations. PK data will be summarized and analyzed based on the PK Analysis Set.

If the results of final ORR from the completed 2nd stage of any arm are encouraging the Review Committee could recommend expansion to add up to an additional 20 eligible subjects

into that arm to further explore the findings (for a total of 40 eligible patients). Refer to Section 9.5.8 for information on the statistical analysis performed for the expansion cohort.

9.5.1 Primary analysis

The primary analysis of ORR will occur approximately 12 weeks after the last patient has initiated treatment. This is planned to ensure the data cut off for ORR analysis follows the 12 week RECIST assessment for the last subject to be treated. However, in the situation where this scan does not occur due to this subject having experienced another progression event (e.g. death) the primary analysis DCO will be when all subjects have been followed for at least 12 weeks or until death if this is earlier. All study endpoints will be analyzed at this time including OS. The Sponsor will determine at that time whether any further follow up for OS would be required.

If the decision is made to close the Arm at the interim analysis the Sponsor will determine the appropriate length of follow up to ensure sufficient data collection for the primary analysis in that Arm.

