6.1 Efficacy assessments

This study will evaluate the primary endpoint of ORR as determined by Investigator assessment according to RECIST 1.1 criteria. Efficacy assessments of PFS, TTR, DoR, and DCR will be derived (by AstraZeneca) using Investigator RECIST 1.1 assessments. In addition, OS will be determined as a secondary efficacy endpoint.

Tumor assessments use images from CT (preferred) or MRI, each preferably with IV contrast, of the chest, abdomen, and pelvis, collected during screening/baseline and at regular (follow-up) intervals during study treatment. Any other areas of disease involvement should be additionally imaged based on the signs and symptoms of individual patients.

The RECIST 1.1 guidelines ([Appendix F](#)) provide a method of assessment of change in tumor burden in response to treatment. Screening/Baseline imaging should be performed no more than 28 days before start of study treatment and ideally should be performed as close as possible to and prior to the start of study treatment. The RECIST 1.1 assessments of baseline images identify target (defined and measurable) and non-target lesions. Each lesion (and any new lesion) is evaluated in subsequent on-treatment follow-up images. This allows determination of follow-up target lesion response, non-target lesion response, and overall timepoint tumor responses (CR, PR, SD, PD, or not evaluable [NE]).

Efficacy for all patients (all arms) will be assessed on images collected either every 6 or 8 weeks \pm 1 week until confirmed objective disease progression or when the patient has been taken off-study. It is important to follow the assessment schedule as closely as possible (refer to the study plans in each arm [screening and treatment period, and follow-up]). If an unscheduled imaging assessment is performed and the patient has not progressed, every attempt should be made to perform the subsequent assessments at his or her next regularly scheduled imaging visit.

According to RECIST 1.1, objective tumor response (CR or PR) should be confirmed preferably at the next scheduled imaging visit and not less than 4 weeks after the visit when the response was last observed.

Patients who have discontinued treatment due to toxicity or symptomatic deterioration, clinical progression, or who have commenced subsequent anticancer therapy will be followed up with tumor assessments until RECIST 1.1-defined PD or until death (whichever comes first) and followed for survival.

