9.4.1.2 Primary endpoint (objective response rate)

ORR (per RECIST 1.1 as assessed by the site Investigator) is defined as the number (%) of patients with a confirmed objective response of CR or PR and will be based on patients in the evaluable set.

A confirmed response of CR/PR means that a response of CR/PR is recorded at 1 visit and confirmed by repeat imaging not less than 4 weeks after the visit when the response was first observed with no evidence of progression between the initial and CR/PR confirmation visit. Therefore, data obtained up until progression, or the last evaluable assessment in the absence of progression, will be included in the assessment of ORR. Any patient who discontinues treatment without progression, receives a subsequent therapy, and then responds will not be included as responders in the ORR.

For sensitivity analysis, ORR may be assessed using the RECIST 1.1 site Investigator tumor data following a modification where any objective progression requires confirmation. Therefore, data obtained up until confirmed progression, or the last evaluable assessment in the absence of a confirmed progression, may be included in the assessment of ORR. Note that the response may be after an unconfirmed progression.

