9.5.7 Interim analysis

An interim analysis will be conducted on each arm. This will assess ORR in all evaluable patients in that arm, to determine whether to progress to stage 2 of the arm. The DCO for the interim analysis will take place approximately 12 weeks after the 10th patient has initiated treatment. If there are CCI responders, then there is a low posterior probability of achieving ORR of at least CCI% in 20 patients and the Review Committee may decide that no further patients will be recruited to the arm. If there are CCI responders out of 10, then an additional 10 patients will be recruited and the final estimate of ORR will be based on 20 patients. If there are CCI or more responders out of 10 patients, then it will be regarded as strong efficacy and the Review Committee may decide to stop recruitment into the particular arm.

The posterior probability of having at least CCI responders in 20 patients for CCI responders in 10 patients is shown below.

	CCI	CCI	CCI	CCI
CCI	CCI %	CCI %	CCI %	CCI %

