6.1 Efficacy assessments

See Section 6.1 of the master protocol.

Efficacy in Arm A will be assessed on images collected at Week 8, Week 12, and then every 8 weeks \pm 1 week until confirmed objective disease progression or off study. The Week 12 scan must be acquired no earlier than 4 weeks from the prior Week 8 scan.

It is important to follow the assessment schedule as closely as possible ([Appendix A Table 2](#)). If an unscheduled imaging assessment is performed and the patient has not progressed, every attempt should be made to perform the subsequent assessments at his or her next regularly scheduled imaging visit.

According to RECIST 1.1, objective tumor response (CR or PR) should be confirmed preferably at the next scheduled imaging visit and not less than 4 weeks after the visit when the response was last observed.

According to RECIST 1.1 modified for confirmation of progression, a confirmatory scan is required following an overall time point assessment of progression, preferably at the next scheduled imaging visit and no earlier than 4 weeks after the previous assessment of PD in the absence of clinically significant deterioration. Treatment will continue between the initial assessment of progression and confirmation for progression.

If a patient discontinues treatment (and/or receives a subsequent anticancer therapy) after the initial assessment of progression, then the patient should continue to be followed with scheduled imaging until confirmed objective disease progression.

Confirmation of progression guidelines are set for the following reasons:

- for patient management and treatment decisions
- in the absence of significant clinical deterioration, to promote the collection of additional scans after the first radiologic RECIST 1.1 assessment of progressive

disease (PD) in order to distinguish pseudoprogression from true radiologic progression, also known as RECIST 1.1 modified for confirmation of progression

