6.3 Efficacy Analysis

See Section 6.1 of the master protocol.

Efficacy in Arm B will be assessed using RECIST 1.1 criteria on images collected at baseline and then every 6 weeks ± 1 week until objective disease progression or off-study.

It is important to follow the assessment schedule as closely as possible (see [Appendix B Table 1](#)). If an unscheduled imaging assessment is performed and the patient has not progressed, every attempt should be made to perform the subsequent assessments at his or her next regularly scheduled imaging visit.

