		Screening	Cycle 1			Subsequent on treatment visits (every 28 days)	Study treatment discontinued	30-day follow-up after last dose of study medication	Follow up for progression and survival	Details in section
			2	3	4					
Visit Number			2	3	4	Visit No.5 onwards				
Day		-28 to -1	1	7	15	Cycle X, Day 1			Every 8 weeks ⁿ	
Visit Window					± 3d	up to 3 days prior to CXD1	up to 7 days after discontinuation	± 7d	± 7d	
Hepatitis B, C and HIV		X								Section 6.3.2. of master protocol
Blood sample for Cytokines			X	X	X	X	X ^m			Section 7.4.1 and 7.4.2 of Appendix C
PK analysis ^g			X	X		Cycles 2 to 6 only				Section 6.4 of master protocol and Appendix C section 7.2
Blood samples for biomarker analysis: plasma and PBMCs isolated from whole blood			X	X	X	X	X ^m			Section 6.6 of master protocol
Peripheral blood for CCI			X			X	X ^m			Section 6.6.1.3 of master protocol and Appendix C section 7.4.1
Peripheral blood for CCI			X		X		X ^m			Sections 6.6.1.2 and 6.6.1.3 of master protocol and Appendix C section 7.4.2
mRNA			X							Appendix C section 7.4.1

		Screening	Cycle 1			Subsequent on treatment visits (every 28 days)	Study treatment discontinued	30-day follow-up after last dose of study medication	Follow up for progression and survival	Details in section	
			2	3	4						
Visit Number			2	3	4	Visit No.5 onwards					
Day		-28 to -1	1	7	15	Cycle X, Day 1			Every 8 weeks ⁿ		
Visit Window					± 3d	up to 3 days prior to CXD1	up to 7 days after discontinuation	± 7d	± 7d		
Tumour assessment (RECIST 1.1) ^h		X	First scan at 8 weeks, then 4 weeks later (i.e. at 12 weeks) and then every 8 weeks (all ± 1 week), from the first day of investigational drug administration for the first 72 weeks, then every 12 weeks ± 1 week hereafter, until disease progression.								Section 6.1 of master protocol
Archival tissue (if available) ⁱ		X								Appendix C Section 7.4.3	
Tumour biopsy with biomarker analyses (optional) ^j		X		X			X ^m			Appendix C Section 7.4.4	
Optional exploratory genetic sample (optional)		X								Appendix C Section 7.4.5	
Ceralasertib and olaparib dispensing			X			X				Appendix C Section 9	
Dispense/review/collect Dosing Diary ^k			X	X	X	X				Appendix C Section 9	
Dosing with ceralasertib ^l			Dosing once daily on Days 1-7 only								Appendix C sections 9.1.1. and 9.2
Dosing with olaparib ^l			Continuous twice daily dosing								Appendix C sections 9.1.2 and 9.2
Post discontinuation anticancer therapy ^o									X	NA	

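### The 12-week cut-off leaves no time to confirm a response first seen at week 12 in the last patients enrolled, so confirmed ORR may be biased downward, mainly at the 10-patient interim

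*Protocol*

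**What the plan says.** **Endpoint.** Section 9.4.1.2 defines ORR by confirmed CR or PR, where a response is "confirmed by repeat imaging not less than 4 weeks after the visit when the response was first observed". The synopsis, master section 6.1 and Appendix A 6.1 give the same minimum but date it differently: "not less than 4 weeks after the visit when the response was last observed". Confirmation at the next scheduled visit is a preference. Section 9.5.2 uses all scans, scheduled or not.

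**Cut-offs.** Section 9.5.1: "The primary analysis of ORR will occur approximately 12 weeks after the last patient has initiated treatment". The reason given is: "This is planned to ensure the data cut off for ORR analysis follows the 12 week RECIST assessment for the last subject to be treated". Section 9.5.7: "The DCO for the interim analysis will take place approximately 12 weeks after the 10th patient has initiated treatment". Section 9.5.8 also uses 12 weeks after the last patient dosed. The only later follow-up named in 9.5.1 is for OS, except that an arm closed at the interim has its follow-up set by the sponsor.

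**Scan calendars.**
- Arm A (Appendix A 6.1 and Table 2): weeks 8, 12, then every 8 weeks, with the added condition "The Week 12 scan must be acquired no earlier than 4 weeks from the prior Week 8 scan".
- Arm B (Appendix B 6.3): "Efficacy in Arm B will be assessed using RECIST 1.1 criteria on images collected at baseline and then every 6 weeks".
- Arm C (Appendix C Table 3): "First scan at 8 weeks, then 4 weeks later (i.e. at 12 weeks) and then every 8 weeks".

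All scans carry a window of 1 week either side.

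**Interim use.** Section 2.2.1 illustrates an early stop at 0/10 and early closure at 3/10 or more. The thresholds in 9.5.7 are redacted.

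**The concern.** The cut-off was chosen so that the last patient has had a week-12 scan. That is long enough to see a response at week 12 but not to confirm one, and only confirmed responses count. The error can run in one direction only: a genuine late response is lost and none is gained. No later ORR update is stated.

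With 10 patients and example thresholds of 0 and 3 responders, one lost responder can change how the interim reads. Treatments whose responses appear at the second scan rather than the first would be hurt most.

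**Working it through.** There is no power or alpha calculation to reproduce, and the confidence-interval and posterior-probability tables are redacted. The check is calendar arithmetic from the protocol, followed by an illustration under stated assumptions.

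**1. When can a response be confirmed?** Take the first later scheduled scan at least 4 weeks after the first response.

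| Arm | First seen | Next scheduled scan | Earliest allowed | By week 12? |
|---|---|---|---|---|
| A, C | week 8 | week 12 | week 12 | yes |
| B | week 6 | week 12 | week 10 | yes |
| A, C | week 12 | week 20 | week 16 | no |
| B | week 12 | week 18 | week 16 | no |

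First-scan responders are covered at nominal timing. Week-12 responders are not.

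**2. Who is exposed?** A patient who started *d* weeks before the last one has 12 + *d* weeks of follow-up at the cut-off. Scheduled confirmation needs 20 weeks (A, C) or 18 weeks (B), so patients with *d* < 8 or *d* < 6 are exposed. With an unscheduled scan at week 16, only *d* < 4 is exposed.

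The protocol gives no accrual pattern. Under even accrual over T weeks, the numbers exposed in Arms A and C are:
- n = 10: 8, 3 or 2 for T = 10, 26 or 52
- n = 20: 6 or 3 for T = 26 or 52
- n = 40: 6 or 3 for T = 52 or 104

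**3. Interim (n = 10).** Let p be the true proportion with a response first seen by week 12 that would go on to be confirmed. Let f be the share of those first seen at week 12, and k the number exposed. No unscheduled confirmation is assumed. Then:

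P(0/10) = (1 − p)^(10 − k) × (1 − p(1 − f))^k

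Expected observed ORR = p(1 − kf/10)

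With p = 0.20 and k = 4:
- No loss: 0.8^10 = 0.107
- f = 0.2: 0.8^6 × 0.84^4 = 0.2621 × 0.4979 = 0.131; expected ORR 18.4%
- f = 0.4: 0.8^6 × 0.88^4 = 0.2621 × 0.5997 = 0.157; expected ORR 16.8%

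P(3 or more of 10), from the sum of the two binomials, falls from 32.2% to 27.4% (f = 0.2) and 22.8% (f = 0.4).

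Range over other assumptions:

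| p | k | f | P(0/10), no loss | P(0/10), with loss |
|---|---|---|---|---|
| 0.1 | 3 | 0.1–0.5 | 34.9% | 36.0–41.0% |
| 0.2 | 3 | 0.1–0.5 | 10.7% | 11.6–15.3% |
| 0.3 | 3 | 0.1–0.5 | 2.8% | 3.2–5.1% |
| 0.2 | 8 | 0.1–0.5 | 10.7% | 13.1–27.5% |
| 0.2 | 10 | 0.2–0.4 | 10.7% | 17.5–27.9% |

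**4. Primary analysis.** Loss in ORR = k × p × f / n, with p = 0.20 and f = 0.1, 0.25, 0.5:
- n = 20, T = 52, k = 3: 0.03f = 0.3, 0.75, 1.5 points
- n = 40, T = 104, k = 3: 0.015f = 0.15, 0.375, 0.75 points
- n = 20, T = 26, k = 6 (faster accrual): 0.06f = 0.6, 1.5, 3.0 points

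**The case against.** The case for leaving the plan alone has real weight.

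- **The problem is narrow.** It needs a first response at week 12 in one of the last patients to start. A reader might infer that ORR is generally undercounted, or that a week-12 response cannot be confirmed before week 18 or 20. The documents support neither: first-scan responders are confirmable by week 12, earlier patients have longer follow-up, and an unscheduled scan could confirm at week 16. Week 16 is still after the cut-off for the last patients.
- **The interim is not mechanical.** Section 9.5.7 says the Review Committee may stop an arm, and section 2.2.1 and the synopsis base decisions on all available data. Section 9.5.2 presents unconfirmed responses alongside confirmed ones. Sections 2.2.1 and 9.2 speak of a minimum of 12 weeks, which allows a later interim but does not require one. A pending response could therefore be noticed, but no text says how it counts. Falling below 3/10 is also not shown to do harm.
- **Losses can be recovered.** A stage 1 response missed at the interim is read again at 20 patients if the arm continues. An arm closed at the interim has sponsor-set follow-up, but that follow-up does not itself reopen recruitment.
- **Arm C.** Its windows alone would allow a gap of 2 to 6 weeks (11 − 9 to 13 − 7) between the first two scans, and Appendix C does not repeat Arm A's sentence. A reader might infer that many week-8 responses in Arm C cannot be confirmed at week 12. That does not hold: master section 6.1 and Appendix F 4.1 already set a 4-week minimum after CR or PR for all patients. Only the wording needs aligning.
- **Week 13.** A week-12 scan taken late in its window is covered by the approximate wording and stated purpose in 9.5.1.
- **Study type.** The trial is exploratory and descriptive, and a short cut-off serves rapid assessment. This limits how serious the point is, but an avoidable one-sided error remains.

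**Conclusion.** The concern holds in this limited form. Under the protocol's own dates, a response first seen at week 12 in a patient who started within about 8 weeks (Arms A, C) or 6 weeks (Arm B) of the last patient has no scheduled confirmatory scan before the cut-off. Unless an unscheduled scan confirms it in time, it is scored as a non-response.

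The effect is mainly at the 10-patient interim. In the central illustration the chance of seeing no responder rises by 2.4 to 5.0 points (13.1 − 10.7 and 15.7 − 10.7), and by more if the arm fills quickly. At the primary analysis it is small under slower accrual. True ORR, the share of week-12 responses and the accrual pattern are all assumptions, since the protocol gives none of them. The direction does not depend on them; the size does.

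**What to change.** 1. **Interim (9.5.7 and synopsis).** State that a CR or PR still awaiting its confirmatory scan counts as a response for the stop/continue decision, or that the decision waits for that scan.
2. **Primary and expansion analyses (9.5.1, 9.5.8 and synopsis).** Set the ORR cut-off so that any response pending at week 12 has reached its next scheduled scan, or progression or death if earlier. With the window this is about week 19 in Arm B (18 + 1) and week 21 in Arms A and C (20 + 1) after the last patient's first dose. Alternatively, keep 12 weeks and state an ORR update at that time.
3. **Minor wording.** Date confirmation from the first observation of response throughout, as 9.4.1.2 does. Align the window wording in Appendix C 7.3 and Table 3 with the 4-week minimum in 6.1 and Appendix F 4.1.

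**Cost.** The ORR cut-off moves by up to 7 weeks in Arm B (19 − 12) or 9 weeks in Arms A and C (21 − 12). Counting pending responses at the interim causes no delay. No extra scans are needed, because those at weeks 18 and 20 are already scheduled.
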